7.9 Conventions

EmBARC (Enhanced Biometric Analysis & Reporting Capability) standard time windowing, imputation rules, and counting rules will be applied.

7.9.1 Decimal Places

The number of decimal places displayed in all listings will be determined by the number of decimal places in the raw data.

Unless otherwise specified, minimum and maximum will be reported to the same precision as the data collected, 1 more decimal place for the mean, median, and SD, and 2 more decimal places for the standard error (SE). The GMR and the lower and upper limits of CI will be displayed to 3 decimal places.

For percent change from baseline data, minimum and maximum will be reported with 0 decimal places; mean, median, and SD will be reported with 1 decimal place; and SE will be reported with 2 decimal places.

The incidence rate will be rounded to 1 decimal place. If the incidence rate is less than 0.1%, then “<0.1” will be displayed.

Three decimal places for ratios will be used for data presentation.

7.9.2 Pharmacokinetic Summaries

In-text Tables

For in-text PK tables, %CV will be reported as integers. For other statistics except for SDs, values of 100 or higher will be presented as integers, values of 10 - <100 will be displayed to 1 decimal place, and values of 1 - <10 will be displayed to 2 decimal places. Values less than 1 will be displayed to 3 decimal places. Ratios will also be displayed to 3 decimal places. Standard deviations will be reported to a precision of 1 decimal place more than the mean.

Handling of Non-Quantifiable Concentrations⁷

For the summaries of plasma concentration-time data, concentrations that are less than the lower limit of quantification (LLOQ) should be displayed as “< LLOQ” in the listings and be treated as missing in summary tables and plots. For the purpose of calculating PK parameters, predose concentrations that are less than LLOQ and concentrations prior to the first quantifiable concentration that are less than LLOQ will be set to zero, and all other concentrations less than LLOQ will be set to missing.

All available plasma concentration-time data and derived PK parameter values will be included in the PK data set and listed accordingly.

Treatment of Outliers

If the predose concentration for a profile is greater than 5% of C_{max}, then the PK parameters for that profile will be excluded from summaries and statistical analysis. Other individual plasma concentrations, if deemed to be anomalous, may be excluded from the analysis following

a review of available documentation (eg, bioanalytical report, clinical data). Any such exclusion will be clearly listed in the study report along with justification for exclusion.

Entire plasma concentration-time profiles for a participant may be excluded following review of available documentation (eg, bioanalytical report, clinical data). However, results of analysis with and without the excluded profiles may be presented in the study report. Any such exclusion will be clearly listed in the study report along with justification for exclusion.

Pharmacokinetic Exclusions

Pharmacokinetic Analysis, Reporting, and Exclusion criteria should follow the BMS PK Harmonization document Version 2.0. Specific guideline for exclusionary criteria for half-life and how other PK parameters are affected for exclusion is under section 6.2 of the BMS PK Harmonization document.

Exclusion of one or more parameters or the entire dataset may be considered due to incomplete profile such as AUC(INF) or when T-HALF cannot be reliably calculated, or there is no sample around the suspected C_{max}. In addition, participants may be excluded from the analysis if they missed doses, had diarrhea, or vomited at or before a time equal to twice the median T_{max} for immediate-release products, or vomited at any time during sampling after the administration of modified-release formulations.

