10.3 Statistical Analyses

The statistical analysis plan will be developed and finalized before database lock and will describe the selection of participants to be included in the analyses, and procedures for accounting for missing, unused, and spurious data. Below is a summary of planned statistical analyses.

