7.2 Study Conduct

Deviations from the study protocol, protocol amendments, and administrative changes will be documented. No potential protocol deviations are defined as being relevant in this healthy volunteer study; listing of relevant protocol deviations will not be provided.

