7.7 Pharmacokinetics

The PK population will be used for all PK listings. The Evaluable PK population will be used for summary statistics and statistical analyses. Analysis will include all valid analyte data for apixaban.

Participant plasma concentration-time profiles will be listed and summarized by treatment and nominal collection time for apixaban. Plots of individual plasma concentration profiles over time will be provided. Overlays of individual plasma concentration profiles over time will be provided by treatment. Plots of mean (+SD) plasma concentration profiles versus time will be presented for apixaban, and all treatments will be superimposed on the same plot.

All individual PK parameters will be listed for apixaban including any exclusions and reasons for exclusion. Summary statistics will be tabulated for each PK parameter by treatment. Geometric means and %CV will be presented for C_{max}, AUC(0-T), AUC(INF), and F_{rel}. Medians and ranges will be presented for T_{max}. Means and SDs will be presented for other PK parameters (ie, T-HALF). Decimal place specifications for summary statistics are described in [Section 7.9](#).

A linear mixed effect model with treatment and period as fixed effects and participant as repeated measures will be fitted to the log-transformed PK parameters (C_{max}, AUC[0-T], and AUC[INF]) for use in estimation of effects and construction of CIs. Kenward-Rogers degrees of freedom will be specified in the model. Initial estimation of the variance/covariance will be based on an unstructured (UN) R matrix assuming no common variances or covariances; however, this UN matrix will be assessed and the more parsimonious compound symmetry (CS) R matrix will be imposed if assumptions of common variances and covariances are reasonable and can be supported by the data. Point estimates and 90% CIs will be exponentiated and results will be reported on the original scale.

Specific details with appropriate SAS code are provided below. Apixaban as 0.1-mg sprinkle capsules (Treatment B) is the test treatment and apixaban as 0.5-mg tablets (Treatment A) is the reference treatment in the analysis.

```
PROC MIXED DATA=PKDATA;  
  BY [log transformed PK parameter such as Cmax, AUC(INF), AUC(0-T)];  
  CLASS TREATMENT PERIOD USUBJID;  
  MODEL LOG_PK = PERIOD TREATMENT / SOLUTION DDFM=KR;  
  REPEATED TREATMENT / SUBJECT = USUBJID TYPE = UN R;  
  LSMEANS TREATMENT / CL ALPHA=0.1;  

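### Does the discretion in SAP 7.9.2 to exclude anomalous concentrations or whole profiles leave the similarity conclusion open?

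*SAP*

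**What the plan says.** Protocol 10.3 leaves the matter to the SAP, which "will describe the selection of participants to be included in the analyses, and procedures for accounting for missing, unused, and spurious data". SAP 7.9.2 then sets several layers of exclusion:

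- **Fixed rule.** If the predose value exceeds 5% of Cmax, that profile's parameters leave the summaries and the statistical analysis.
- **Single values.** "Other individual plasma concentrations, if deemed to be anomalous, may be excluded from the analysis following" a review of documentation.
- **Whole profiles.** "Entire plasma concentration-time profiles for a participant may be excluded following review of available documentation", the examples being the bioanalytical report and clinical data. For these, "results of analysis with and without the excluded profiles may be presented in the study report".
- **Named grounds.** "Exclusion of one or more parameters or the entire dataset may be considered due to incomplete profile", and "participants may be excluded from the analysis if they missed doses, had diarrhea, or vomited" within a stated window.
- **External criteria.** Exclusion criteria are to follow version 2.0 of a sponsor PK harmonization document, which is cited but not reproduced.

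Outlier exclusions must be listed in the study report with their justification. SAP 7.7 adds that "All individual PK parameters will be listed for apixaban including any exclusions and reasons for exclusion". SAP 6.3 and 7.7 assign summary statistics and statistical analysis to the Evaluable PK population. SAP 5 concludes similarity when the 90% CIs for Cmax and AUC lie within 80% to 125%.

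**The concern.** The primary conclusion rests on a few confidence limits from about 28 people, treatment is known to everyone, and the documents reviewed before an exclusion include the concentrations. The SAP does not say in its own text what counts as anomalous, who decides, or by when. The display with and without excluded profiles is optional, and none is mentioned for single concentrations. SAP 5 names no analysis set. A participant with a complete profile and no deviation meets the Evaluable PK definition in 6.3, yet could have that profile removed under 7.9.2. If the two analyses disagreed, a reader might ask which one counts. If exclusions were chosen by their effect on the result, the chance of wrongly concluding similarity would exceed the nominal 5%.

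A further wording point is that SAP 7.2 states "No potential protocol deviations are defined as being relevant in this healthy volunteer study", while 6.3 removes participants for deviations that affect PK.

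**Working it through.** **1. Which result decides, from the text.** SAP 6.3 says only participants with evaluable PK data enter the statistical analysis. SAP 7.7 says the Evaluable PK population is used for that analysis. SAP 7.9.2 takes values and profiles out of the analysis. Together, the model is fitted to evaluable data after exclusions, and the comparison with and without them is supplementary. A cross-reference between 6.3 and 7.9.2 is missing, but no second primary data set is created. SAP 7.2 concerns a listing of relevant deviations and defines no analysis set, so it does not compete with 6.3.

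**2. Inputs (SAP 5).** Within-subject CV is 18% for Cmax and 12% for AUC; n = 28; limits are 0.80 and 1.25; the 90% CI corresponds to two one-sided 5% tests.

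**3. The plan's own power.**
- σw = √ln(1 + 0.18²) = 0.1786
- SE = σw × √(2/28) = 0.0477, with 26 df
- Exact two one-sided tests power for Cmax at a true ratio of 1.10: 83.2% (stated 83%)
- AUC, CV 12%: 98.8% (stated 99%)
- Overall, as the product of the three: 81.2% (stated 81%)

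All Cmax and AUC rows of the table reproduce.

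**4. How far one participant can move the limit.** The SD of a log ratio is √2 × 0.1786 = 0.2525. Suppose one participant lies 2.5 sample SD above the mean.
- Removal shifts the mean by 2.5 × 0.2525 / 27 = 0.0234.
- The variance falls to (27 − (28/27) × 2.5²) / 26 = 0.789 of its value, so the SD becomes 0.2243.
- The paired 90% half-width goes from 1.703 × 0.2525/√28 = 0.0813 to 1.706 × 0.2243/√27 = 0.0736.
- The upper limit falls by 0.0234 + 0.0077 = 0.0311 on the log scale, about 3%.

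This can matter only when the limit is already close to 125%.

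**5. False similarity for Cmax at a true ratio of 1.25.** Simulated paired log ratios, n = 28, participant removed from both periods, AUC not limiting:

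| Exclusion behaviour (assumed) | False similarity |
|---|---|
| None, or unrelated to the result | 5.0% |
| Most unfavourable participant dropped only if the full analysis fails and beyond 2.5 SD | 6.4% |
| Same, beyond 3 SD | 5.3% |
| Same, beyond 3.5 SD | 5.0% |
| Most unfavourable participant always dropped | 11.9% |

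A participant beyond 2.5 SD arises by chance in 11% of trials, and beyond 3 SD in 1.4%. The AB/BA model with a period effect gives 5.0%, 6.3%, 5.2%, 5.0% and 11.8% in the same order, and repeat runs agree within 0.2 points. If AUC is also truly at 1.25, the joint rate is 1.2% to 2.4% with all data and at most 2.9% to 6.1% after the worst drop (correlation 0.5 to 0.8).

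**6. Exclusions unrelated to the result.** Error stays at 5%. Cmax power at 1.10 goes from 83.2% (n = 28) to 81.9% (27) and 80.6% (26).

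**7. The price of the stricter rule.** Suppose value-only exclusions could never carry the conclusion, and one participant's B/A Cmax ratio is halved with no documented cause. Keeping that participant lowers Cmax power from 96.9% to 87.4% at a true ratio of 0.95, and from 99.6% to 98.5% at 1.00.

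**The case for a change.** The strongest case for a change is that a listing discloses a choice but does not fix the data set in advance, and that Protocol 10.3 promised procedures for spurious data. For whole profiles the outlier paragraph gives no ground beyond a review. The sponsor document may hold criteria, but its one specific pointer in 7.9.2 concerns half-life and its effect on other parameters. The decision can also be fragile: at a true ratio of 1.10, some single participant exists whose removal reverses the Cmax decision in about 18% of simulated trials (under 1% at 1.00). Tighter wording would cost little.

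It stands that the SAP text leaves the criterion, decider and time point unwritten and that 6.3 and 7.9.2 do not refer to each other. The rest carries less weight. The SAP does not say that exclusions follow the treatment comparison; the documents named are source records, not ratios or intervals. The 18% counts trials in which a suitable participant exists, not trials in which a documented review would remove that person. All concentrations and derived parameters stay in the data set and are listed, so the alternative result can be recomputed even if it is not displayed. Making that display mandatory would add transparency but alter no deciding result.

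**Conclusion.** No change to the plan follows. On a natural reading of SAP 6.3, 7.7 and 7.9.2 together, the Evaluable PK analysis after exclusions decides similarity. The unwritten details are ones a PK analyst fills through documentary review, stated justification and the cited sponsor criteria. Followed as written, without choosing exclusions by outcome, the plan holds its 5% error rate. Under assumed outcome-driven dropping of one participant beyond 2.5 SD or more, the rate is at most about 6.4%. The figure near 12% needs the worst participant always to be deleted, which the SAP does not describe. The one proposal that would change the deciding result, barring value-only exclusions from it, is a fair trade-off rather than a correction: about 10 points of Cmax power in the halved-ratio example at 0.95, against about 1.4 points of error (6.4% − 5.0%).

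These sizes rest on the planned CVs, n = 28 and one participant removed from both periods. They do not model loss of single concentrations or of one period only. The documents give no expected number of exclusions, and the content of the sponsor PK document could not be checked.

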8 CONTENT OF REPORTS

Statistical components for the CSR will be based on the content of this SAP. Details of the tables, listings, and figures to be prepared for the final CSR will be included in a study-specific Data Presentation Plan (DPP).

9 List of Abbreviations

Table 9-1: List of Abbreviations	
AE	adverse event
AUC	area under the concentration-time curve
AUC(0-T)	area under the plasma concentration-time curve from time zero to time of last quantifiable concentration
AUC(INF)	area under the plasma concentration-time curve from time zero extrapolated to infinite time
BMS	Bristol-Myers Squibb
BP	blood pressure
CI	confidence interval
Cmax	maximum observed concentration
CSR	clinical study report
%CV	coefficient of variation
FXa	Factor Xa
ECG	electrocardiogram
Frel	relative bioavailability
GMR	geometric mean ratio
ICF	informed consent form
LLOQ	lower limit of quantification
N	number of participants
PT	preferred term
PK	pharmacokinetic(s)
QTcF	QT interval corrected for heart rate using Fridericia's formula
SAE	serious adverse event
SAP	statistical analysis plan
SD	standard deviation
SE	standard error
SOC	system organ class
T-HALF	terminal half life
Tmax	time of maximum observed plasma concentration
UN	unstructured

[REDACTED]

- [REDACTED]
- [REDACTED]
[REDACTED]
- [REDACTED]
[REDACTED]
- [REDACTED] [REDACTED] [REDACTED] [REDACTED] [REDACTED] [REDACTED] [REDACTED] [REDACTED]
[REDACTED]
[REDACTED] [REDACTED] [REDACTED] [REDACTED] [REDACTED] [REDACTED] [REDACTED] [REDACTED]
[REDACTED]
- [REDACTED]
[REDACTED] [REDACTED] [REDACTED] [REDACTED] [REDACTED] [REDACTED] [REDACTED] [REDACTED]
[REDACTED]
- [REDACTED]
[REDACTED]
[REDACTED]
- [REDACTED]
[REDACTED]
